7. DISCONTINUATION OF STUDY INTERVENTION AND PARTICIPANT DISCONTINUATION/WITHDRAWAL

7.1. Discontinuation of Study Intervention

It may be necessary for a participant to permanently discontinue study intervention. Reasons for permanent discontinuation of study intervention may include the following:

- Objective disease progression;
- Global deterioration of health status requiring discontinuation;
- Unacceptable toxicity;
- Pregnancy;
- Significant protocol violation;
- Lost to follow-up;
- Participant refused further treatment;
- Study terminated by sponsor;
- Death;

Note that discontinuation of study intervention does not represent withdrawal from the study. If study intervention is permanently discontinued, the participant will remain in the study to be evaluated for safety follow-up and survival follow-up (Part 2). See the [SOA](#) for data to be

collected at the time of discontinuation of study intervention and follow-up for any further evaluations that need to be completed.

In the event of discontinuation of study intervention, it must be documented on the appropriate CRF/in the medical records whether the participant is discontinuing further receipt of study intervention or also from study procedures, posttreatment study follow-up, and/or future collection of additional information.

Safety Follow-Up:

At least 28 calendar days, and no more than 35 calendar days after discontinuation of study intervention, participants will return to undergo review of concomitant treatments, vital signs, and assessment for resolution of any treatment related AEs. Participants continuing to experience AEs at this point following discontinuation of treatment will continue to be followed at least every 4 weeks until resolution or determination, in the clinical judgment of the investigator, that no further improvement is expected. If the unresolved AE is considered by the investigator as possibly related to or associated with ADA formation, the participant will be asked to return for drug concentration and ADA blood sampling at up to 3-month intervals, until the last follow-up of the AE.

For part 2 of the study, survival status will be collected by telephone every 3 months until death, or up to 24 months after first dose of the last participant.

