10.13. Appendix 13: Immune Related Response Criteria Derived from RECIST 1.1 (irRECIST)

Increasing clinical experience indicates that traditional response criteria may not be sufficient to fully characterize activity in this new era of targeted therapies and/or biologics.

The irRECIST tumor assessment system has been developed to incorporate delayed or flare type- responses into the RECIST v1.1 ([Nishino et al, 2014](#)).

For irRECIST, only target and measurable lesions are taken into account. In contrast to RECIST v1.1, irRECIST:

- Requires confirmation of both progression and response by imaging at least 4 weeks from the date first documented, and
- Does not necessarily score the appearance of new lesions as progressive disease if the sum of lesion diameters of target lesions (minimum of 10 mm longest diameter per non-nodal lesion and 15 mm shortest diameter per nodal lesion, maximum of 5 target lesions, maximum of 2 per organ) and measurable new lesions does not increase by ≥20%.

The same method of assessment and the same technique should be used to characterize each identified and reported target lesion(s) at baseline and throughout the trial.

irRECIST is defined as follows:

- Overall immune-related complete response (irCR): Complete disappearance of all lesions (whether measurable or not) and no new lesions. All measurable lymph nodes also must have a reduction in short axis to <10 mm.
- Overall immune-related partial response (irPR): Sum of the diameters (longest for non-nodal lesions, shortest for nodal lesions) of target and new measurable lesions decreases ≥30%.
- Overall immune-related stable disease (irSD): Sum of the diameters (longest for non-nodal lesions, shortest for nodal lesions) of target and new measurable lesions is neither irCR, irPR, (compared to baseline) or immune-related progressive disease (irPD, compared to nadir).
- Overall immune-related progressive disease (irPD): Sum of the diameters (longest for non-nodal lesions, shortest for nodal lesions) of target and new measurable lesions increases ≥20% (compared to nadir), confirmed by a repeat, consecutive observation at least 4 weeks from the date first documented.

New measurable lesions: Incorporated into tumor burden (ie, added to the target lesion measurements). A lymph node has to be ≥15 mm in short axis to be a measurable new lesion

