and its short axis measurement is included in the sum. Up to 2 new lesions per organ and up to 5 new lesions in total can be added to the measurements.

New non-measurable lesions: Do not define progression but preclude irCR.

Overall responses derived from changes in index, nonindex, and new lesions are outlined in Table 20.

[figure not shown]
Table 20. Overall Response Derived from Changes in Index, Non-index and New Lesions

Measurable Response	Nonmeasurable- Response		Overall Response Using irRECIST ^b
Index and New Measurable Lesions (Tumor Burden) ^a	NonIndex- Lesions	Measurable Lesions	
Decrease 100%	Absent	Absent	irCR
Decrease 100%	Stable	Any	irPR
Decrease 100%	Unequivocal progression	Any	irPR
Decrease $\geq 30\%$	Absent/stable	Any	irPR
Decrease $\geq 30\%$	Unequivocal progression	Any	irPR
Decrease $< 30\%$ and increase $< 20\%$	Absent/stable	Any	irSD
Decrease $< 30\%$ and increase $< 20\%$	Unequivocal progression	Any	irSD
Increase $\geq 20\%$	Any	Any	irPD

a. Decrease assessed relative to baseline.

b. Response (irCR and irPR) and progression (irPD) must be confirmed by a second, consecutive assessment at least 4 weeks apart.

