### Part 2 Dose Expansion

The Part 2 dose expansion phase will enroll participants into 3 cohorts detailed as follows:

- **Part 2A (N=20):** PF-07260437 as monotherapy in participants with HR+ HER2- BrCa showing high B7-H4 expression, 2L+ who have progressed after at least 1 line of standard of care CDK4/6 inhibitor and 1 line of standard of care endocrine treatment. De novo paired pre- and on-treatment biopsies are mandatory for 5 participants.
- **Part 2B (N=20):** PF-07260437 as monotherapy in participants with HR+ HER2- BrCa, 2L+ who have progressed after at least 1 line of standard of care CDK4/6 inhibitor and 1 line of standard of care endocrine treatment, or 2L+ TNBC who have progressed after at least 1 line of SOC systemic therapy (eg 1L chemotherapy in combination with an immune checkpoint inhibitor if PD-L1+ or chemotherapy alone if PD-L1 negative/low). Approximately 10 HR+ HER2- BrCa and approximately 10 TNBC participants should be enrolled. De novo paired pre- and on-treatment biopsies are mandatory for approximately 5 HR+ HER2- BrCa participants and 5 TNBC participants. No biomarker selection based on B7-H4 expression.
- **Part 2C (N=20):** PF-07260437 as monotherapy in participants with TNBC showing high B7-H4 expression, 2L+ who have progressed after at least 1 line of SOC systemic therapy (eg, 1L chemotherapy in combination with an immune checkpoint inhibitor if PD-L1 positive or chemotherapy alone if PD-L1 negative/low). De novo paired pre- and on-treatment biopsies will be mandatory for 5 participants.

Depending on the results of preclinical combination in vivo efficacy data, emerging clinical monotherapy safety and efficacy, PF-07260437 combination cohorts may be added, including combination with CDK4/6 inhibitor and/or endocrine therapies in HR+ HER2- BrCa and combination with checkpoint inhibitors in TNBC.

All participants will undergo up to 28 days of screening prior to first dose. Eligible participants will then receive study intervention for up to 2 years, or until disease progression defined by irRECIST, unacceptable toxicities, a decision by the participant (withdrawal of consent or no longer willing to participate) or investigator to discontinue treatment, or study termination. Note: If a participant is classified as having PD during an on-treatment tumor assessment, then confirmation of PD by a second scan in the absence of rapid clinical deterioration is required per irRECIST.

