### 6.2.4 Efficacy Analysis

Response Evaluable Set will be used for all response-related analyses including ORR, DoR, PFS, and TTP (RECIST, irRECIST). Tumor response will be presented in the form of participant data listings that include, but are not limited to tumor type, tumor response at each visit, and best overall response. Immune related response by irRECIST will be calculated and reported similarly to RECIST response. OS will be reported on the Full Analysis Set as well as on the mITT.

Data will be summarized (also graphically where appropriate) and listed by expansion cohort.

- **Overall Response Rate (ORR)**

- Overall response rate (ORR) is defined as the proportion of patients with a BOR of confirmed CR or confirmed PR by Investigator assessment in intracranial metastasis and extracranial lesions per mRECIST v1.1 (or RANO for glioblastomas) and RECIST v1.1, respectively.

- **Duration of Response (DOR)**

- Duration of response is defined as the time from start date (which is the date of first documentation of PR or CR) to date of first documentation of objective progression or death. Both confirmed DOR and unconfirmed DOR (uDOR) will be determined and reported separately for the subset of participants with a confirmed and unconfirmed objective response of CR or PR (defined below). DOR will be derived for Intracranial/RANO response rate, extracranial response rate and ORR.

- **Best Overall Response (BOR)**

- **Complete Response (CR):** Two objective statuses of CR a minimum of 4 weeks apart documented before PD.
- **Partial Response (PR):** Two objective statuses of PR or better (PR followed by PR or PR followed by CR) a minimum of 4 weeks apart documented before PD, but not qualifying as CR. Sequences of PR- Stable- PR are considered PRs as long as the two PR responses are observed at a minimum of 4 weeks apart.
- **Stable Disease (SD) (applicable only to patients with measurable disease at baseline):** At least one objective status of stable disease or better documented at least 6 weeks after start of treatment and before PD but not qualifying as CR or PR.
- **Non-CR/non-PD (applicable only to patients with non-measurable disease at baseline):** at least one non-CR/non-PD assessment (or better) documented at least 5 weeks after start of treatment and before first documentation of PD (and not qualifying for CR or PR).

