### Progression-free Survival (PFS)

- Analysis set: Response Evaluable

Progression-free survival (PFS) is defined as the time from date of the first dose of study treatment to the earliest documented disease progression by Investigator assessment, or death due to any cause, whichever occurs first. If a patient has not had a PFS event at the time of the analysis cutoff or at the start of any new anticancer therapy, PFS is censored at the date of last adequate tumor assessment.

PFS will be calculated as follows:

$$\text{PFS (months)} = (\text{date of event or censoring} - \text{date of first dose} + 1) / 30.4375$$

The censoring and event date options to be considered for PFS analysis are presented in Table 2.

PFS time will be estimated using the Kaplan-Meier method. The PFS rate at 3, 6, 9, 12, 15 and 18 months will be estimated with corresponding 2-sided 95% CIs.

Frequency (number and percentage) of participants with each event type (PD or death) and censoring reasons will be presented along with the overall event and censor rates. Reasons for censoring will be summarized according to the categories in [Table 3](#). In addition, time to progression/censoring, event, and censoring reasons will be listed.

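### The SAP leaves the irRECIST progression event undefined; read literally, a first irPD that is never confirmed is censored before the progression, which biases irRECIST PFS and DOR upward

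*SAP*

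**What the plan says.** **What irPD is.** Protocol Appendix 13 defines irPD as an increase of at least 20% over nadir, "confirmed by a repeat, consecutive observation at least 4 weeks from the date first documented". The footnote to Table 20 repeats it: "Response (irCR and irPR) and progression (irPD) must be confirmed by a second, consecutive assessment at least 4 weeks apart". Neither place gives an exception.

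**What the treatment rule says.** SAP 2.2 (Part 2 Dose Expansion), like Protocol 4.1, words it differently: "confirmation of PD by a second scan in the absence of rapid clinical deterioration is required per irRECIST". Protocol 7.1 lists "Objective disease progression" among the reasons to stop treatment and does not mention confirmation.

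**When scans happen.** Protocol 8.1.1 schedules scans every 8 weeks for 6 months, then every 12 weeks. It adds scans when progression is suspected, and one at withdrawal unless a scan was done in the previous 4 weeks. No scan is scheduled 4 weeks after a first irPD.

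**How the SAP analyses it.** SAP 6.2.4 applies irRECIST to ORR, DoR, PFS and TTP. The instruction is "Immune related response by irRECIST will be calculated and reported similarly to RECIST response". PFS runs to the first progression documented by the investigator or death, DOR likewise, and TTP to progression alone. Table 2 (PFS and DOR) sends participants with no PD, or with new therapy before PD, to the last adequate assessment that showed no PD. The PFS text says only that "PFS is censored at the date of last adequate tumor assessment". A missing-data bullet in the same section drops data collected after study treatment stops.

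**The concern.** A participant whose first irPD scan ends treatment may never have a second scan. If irPD then formally does not exist, the participant falls into the no-PD or new-therapy row of Table 2 and is censored at a date before the progression that caused the stop. Censoring would be tied to the event being measured, which Kaplan-Meier estimation does not allow for.

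irRECIST PFS, TTP and DOR are secondary endpoints of Part 2, and Protocol 4.3.9 bases the RP2D partly on early signs of efficacy. An irRECIST PFS lying above the RECIST 1.1 PFS could be taken for delayed immune benefit when part of the gap comes from the censoring. Two programmers following this SAP could also produce different results from the same data.

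**Working it through.** **1. Follow one participant through the text.** First irPD at a scheduled scan; treatment stops two weeks later; new therapy starts.
- Appendix 13: no second scan, so no irPD.
- Protocol 8.1.1: the withdrawal scan may be skipped, because one was done within 4 weeks.
- SAP 6.2.4 missing-data bullet: a later scan, even if obtained, may be dropped. Protocol Appendix 12 asks sites to document progression after discontinuation, so the two texts pull apart.
- Table 2: new therapy before PD, so the participant is censored at the last scan showing no PD.

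**2. The same participant without new therapy who dies.** Table 2 counts a death after at most one missing assessment as an event for PFS and DOR. On an 8-week grid that means a death less than 16 weeks after the irPD scan. The event is late but is not lost. For TTP, death is not an event.

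**3. TTP.** Table 2 is titled for PFS and DOR only. SAP 5.4 refers to Appendix 1 for PFS and TTP censoring, but Appendix 1 contains only the OS table.

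**4. Size of the bias (illustration).** The plan states no figure for irRECIST PFS, so there is none to reproduce.

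Inputs from the documents: 8-week scans, and a median PFS of 5.4 months (Protocol 4.2.2, a first-line TNBC figure). Assumptions: exponential times; a share *u* of first irPDs unconfirmed, independent of timing; a participant unconfirmed at the first scan is censored at first dose.

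- Scan interval: 56/30.4375 = 1.84 months.
- Survival per interval: s = 2^(−1.84/5.4) = 0.790, so h = 1 − s = 0.210.
- All first irPDs counted: at 6 months three scans (weeks 8, 16, 24) have passed, so PFS = s³ = 0.49.
- Literal reading: unconfirmed cases leave at the previous scan. Per unit at risk, the risk set at each scan is 1 − u·h and the events are (1 − u)h. The Kaplan-Meier factor is 1 − (1 − u)h/(1 − u·h) = s/(1 − u·h).
  - u = 10%: (0.790/0.979)³ ≈ 0.525
  - u = 25%: (0.790/0.947)³ ≈ 0.58
  - u = 40%: (0.790/0.916)³ ≈ 0.64

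A simulation of 40,000 participants per scenario gave 0.527, 0.576 and 0.637, in agreement. Adding deaths (assumed median survival after progression 3 months, half starting new therapy) gave:

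| 6-month PFS, median 5.4 months | u = 10% | u = 25% | u = 40% |
|---|---|---|---|
| First irPD counted | 0.49–0.50 | 0.49 | 0.49 |
| Literal censoring | 0.53 | 0.58 | 0.64 |
| Literal, early deaths as events | 0.53 | 0.56 | 0.61 |

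With an assumed median of 3.5 months, 0.34 becomes 0.37, 0.43 and 0.49 under literal censoring, and 0.36, 0.41 and 0.46 with deaths counted.

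**5. Does the censoring date matter?** The PFS text does not require the last assessment to show no PD. If unconfirmed cases are censored at the irPD scan itself, the factor is 1 − (1 − u)h. This gives (1 − 0.9 × 0.210)³ = 0.53 at 10% and (1 − 0.75 × 0.210)³ = 0.60 at 25%. The direction is the same.

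**6. Scale.** With about 20 per cohort, the standard error near 0.49 is √(0.49 × 0.51/20) = 0.11. A 25% unconfirmed share moves the estimate by 0.07 to 0.09, or 0.6 to 0.8 of a standard error.

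**The case against.** The strongest reply is that nothing in the SAP expressly censors an unconfirmed irPD. PFS, TTP and DOR all refer to the first documented progression, so handling irRECIST like RECIST could mean that the first irPD scan is the event. On that reading the bias from this source is zero. This stands, and it is why the defect is an undefined event and not a stated wrong rule. The quoted instruction also speaks of response, not of time-to-event endpoints.

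A reader might infer that rapidly deteriorating participants are always lost. The documents do not support that. The treatment wording can be read as waiving confirmation for them, and what is certain is only that it does not match Appendix 13. A reader might also infer that the worst progressors all leave without an event. Table 2 counts most early deaths without new therapy for PFS and DOR, so that is too broad.

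Confirmation will often be obtained, since treatment is planned to continue until irRECIST progression, and a withdrawal scan at least 4 weeks after the first irPD can itself confirm it. The missing-data bullet stands under tumor response, so applying it to PFS is an inference. RECIST 1.1 versions, which need no confirmed PD, are reported alongside, nothing is tested, and SAP 6.2.4 lists progression and death dates by participant. These points lower the severity. They do not supply the missing rule.

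**Conclusion.** The concern holds as a gap with a predictable direction. The SAP does not define the irRECIST progression event, its date or the handling of an unconfirmed first irPD. Applied literally, its definitions censor participants who stop or switch before a second scan, and irRECIST PFS and DOR are then too high. For TTP the censoring rule is missing altogether.

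The size cannot be fixed from the documents. In the illustration, 6-month PFS rises from 0.49 to about 0.53 at 10% unconfirmed and to 0.56–0.58 at 25%. This rests on an assumed unconfirmed share, exponential times and a first-line median, whereas Part 2 enrols later lines. DOR was not simulated; its direction follows from sharing Table 2. Shifts in the median should not be cited: 5.4 months lies just before the 24-week scan, so a small change moves the median a whole scan interval.

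A claim that irRECIST PFS will be biased, or that the SAP orders this censoring, goes beyond the text. Severity is moderate: descriptive secondary endpoints, about 20 participants per cohort, with RECIST 1.1 results beside them.

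**What to change.** In SAP 6.2.4 and Table 2, add for irRECIST:
- Date irPD at its first documentation.
- Count a first irPD as an event at that date if it is confirmed, or if no later adequate assessment exists (deterioration, discontinuation, new therapy or death).
- Do not count it if the next scan contradicts it.
- Make the censoring date in the PFS text agree with Table 2.

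Also add a censoring table for TTP and correct the reference in SAP 5.4. Reconcile the confirmation wording in Protocol 4.1 and SAP 2.2 with Appendix 13, and the exclusion of post-discontinuation data in SAP 6.2.4 with Protocol Appendix 12. Report the number of unconfirmed irPDs per cohort, with a sensitivity analysis under the other handling.

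The cost is SAP wording and programming, plus a wording clarification in the protocol if the confirmation text is changed there. No new data are needed.

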**Table 1. Analysis Sets**

Participant Analysis Set	Description
Full Analysis Set (FAS)	All enrolled participants.

Participant Analysis Set	Description
Safety Analysis Set (SAS)	All enrolled participants who receive at least 1 dose of study intervention. Unless otherwise specified the safety analysis set will be the default analysis set used for all analyses.
Per Protocol Analysis Set	All enrolled participants who do not have major protocol deviations during the course of the study
DLT Evaluable Set	All enrolled participants who had at least 1 dose of study treatment and either experienced DLT or do not have major protocol deviations during the DLT observation period and received either 100% of dosing in cycle 1 (no priming regimen) or 100% of dosing in cycle 1 and cycle 2 (priming regimen)..
mITT Population	All enrolled participants who have received at least 1 dose of study medication; have a baseline assessment and at least 1 post baseline assessment;
Response Evaluable set	The response evaluable population will include all participants who received at least one dose of study treatment and had measurable disease at baseline and at least one post baseline disease assessment.
PK Parameter Set	All enrolled participants treated who do not have protocol deviations influencing PK assessment and have sufficient information to estimate at least 1 of the PK parameters of interest.
PK Concentration Set	All enrolled participants who are treated and have at least 1 analyte concentration above the lower limit of quantitation.

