### Overall Survival (OS)

- Analysis set: Full Analysis Set

OS will be calculated in months as follows:

$$\text{OS (months)} = (\text{date of death or censoring} - \text{date of first dose} + 1)/30.4375$$

OS time will be estimated using the same Kaplan-Meier method. The OS rate at 6, 12, 18, 24, 30 and 36 months will be estimated with corresponding 2-sided 95% CIs.

Frequency (number and percentage) of patients with death events and censoring reasons will be presented by cohort along with the overall event and censor rates. The event and censoring reasons are as follows:

- Death:
  - Death due to COVID-19.
  - Ongoing and no death.
  - Withdrawal of consent.
  - Lost to follow-up.
- The OS time or censoring time and the reasons for censoring will also be presented in a patient listing.

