## 9. APPENDICES

### Appendix 1 Time to Event Data Analysis Censoring Rules

**Table 4 OS Outcome and Event Dates**

Situation	Date of Death/Censoring	Outcome
Alive	Date of Last Contact	Censored
Death due to any cause	Date of Death	Event

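### Part 2 OS is also to be reported on an mITT set that can leave out early deaths, and the FAS has no first-dose origin for anyone enrolled but never dosed

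*SAP*

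**What the plan says.** The efficacy overview in SAP 6.2.4 says that "OS will be reported on the Full Analysis Set as well as on the mITT". SAP 3.2 and Protocol 9.3.3 carry the same sentence. The Overall Survival subsection of the SAP, where the endpoint is specified, has only "Analysis set: Full Analysis Set" and does not mention the mITT.

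SAP Table 1 defines the sets involved:

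- FAS: "All enrolled participants", with no dosing condition.
- Safety Analysis Set: "All enrolled participants who receive at least 1 dose of study intervention". It is the default set for analyses that name no other.
- mITT: "All enrolled participants who have received at least 1 dose of study medication; have a baseline assessment and at least 1 post baseline assessment". The kind of assessment is not stated.

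The OS formula counts from the date of first dose to death or censoring. SAP Appendix 1 Table 4 censors living participants at "Date of Last Contact" and treats death from any cause as an event. Neither place says what to do with a participant who has no first dose.

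**The concern.** Two separate matters arise.

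The first is the mITT set. Membership depends on something that happens after the OS clock starts. A dosed participant who dies before the qualifying assessment leaves the set because of that death, and everyone who stays has survived to the assessment by construction. This is immortal time, and it can only move the OS curve upward. The exclusion is not needed for data reasons: Protocol Table 5 and Section 7.1 collect Part 2 survival status by telephone every three months, whether or not a scan was done. The SAP expects such participants to exist, since early death with no post-baseline assessment is one of its listed reasons for a non-evaluable best response.

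The second is the match between set and origin. The FAS is defined by enrolment and OS by first dose. For an enrolled participant who was never dosed, the formula has no start date, and a programmer would have to drop the participant or choose an origin without a rule.

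What is at stake is the reported OS medians and landmark rates for the three expansion cohorts. The SAP also disagrees with itself on whether an mITT OS result will be produced, and in an open-label study that should be settled before the data are analysed.

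**Working it through.** The documents give no OS sample size, event count or expected median for Part 2, so there is no stated figure to reproduce. The check compares the definitions and then sizes the mITT condition under stated assumptions.

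**Inputs**

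- OS origin: first dose (SAP, Overall Survival).
- First scheduled post-baseline tumour assessment: 8 weeks from C1D1, window ±7 days (Protocol 8.1.1).
- Cohort size: about 20 (Protocol 9.5.2).
- OS distribution: exponential. This is an assumption.
- Median OS: 6 to 17.5 months. This is an assumption. The upper value is the first-line TNBC figure quoted in Protocol 4.2.2, whereas Part 2 enrols later-line participants. The lower value has no source in the documents.

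**Formulas**

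Let t0 be the time by which a participant must be alive to qualify, and m the true median.

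- Share of dosed participants who die before t0: 1 − 0.5^(t0/m).
- Survival at t among those who qualify: S(t)/S(t0).
- Median among those who qualify: m + t0, because the exponential has no memory.

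**Reading A: the assessment is the week-8 scan.** t0 = 56/30.4375 = 1.84 months.

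| True median (months) | Dropped | Of 20 dosed | mITT median (months) | 12-month OS, all dosed → mITT |
|---|---|---|---|---|
| 6 | 19.1% | 3.8 | 7.84 | 25% → 31% |
| 9 | 13.2% | 2.6 | 10.84 | 40% → 46% |
| 12 | 10.1% | 2.0 | 13.84 | 50% → 56% |
| 17.5 | 7.0% | 1.4 | 19.34 | 62% → 67% |

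For a median of 6: 1 − 0.5^(1.84/6) = 0.191, and 12-month OS is 0.250/0.809 = 0.309. The chance that a cohort of 20 loses at least one participant in this way is 99% at a median of 6 and 77% at 17.5. Moving t0 across the scan window (days 49 to 63) changes the shift in the median to between 1.6 and 2.1 months. A simulation with 20 participants and t0 = 56 days gave typical sample medians of 6.0 → 7.8, 12.1 → 13.9 and 17.6 → 19.4 months.

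**Reading B: any post-baseline visit counts.** Protocol Table 5 schedules vital signs and laboratory tests on Day 2, so t0 can be 1 day, or 0.03 month. At most 0.4% are dropped and the median moves by about 0.03 month.

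**FAS.** It contains every dosed participant, so no early death among them is lost and the shift from this source is zero. Protocol 5.4 defines screen failures as not enrolled, so they are outside the set. What remains is participants enrolled but never dosed. Their number is not given and cannot be derived. If there are none in Part 2, the FAS and the Safety Analysis Set are the same people and the FAS curve is already the intended one.

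**The case against.** A reader might infer that both OS sets are unsuitable and that neither result would be correct. The documents do not support that. The FAS is the only set named in the Overall Survival subsection, it keeps all early deaths among dosed participants, and its fault is confined to undosed members of unknown number. The explicit procedure confirming enrolment before any dose (Protocol 6.3.1) is for Part 1, while OS is a Part 2 endpoint.

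A reader might also take a 1.8-month inflation of the mITT median as established. It is not, for three reasons.

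- Table 1 asks for a disease assessment only in the Response Evaluable set; the mITT row omits that word, which leans towards Reading B. Against this, SAP 6.2.4 uses the same term for tumour scans when it lists reasons for non-evaluability. The point is open.
- Even under Reading A, week 8 is not the earliest possible scan. Protocol 8.1.1 also requires imaging when progression is suspected and at withdrawal from treatment, so some participants who die before week 8 would already have qualified.
- A constant hazard from day 1 probably overstates early deaths, given entry limited to ECOG 0 or 1 and exclusion of visceral spread that is life-threatening in the short term.

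The consequences are limited as well. There is no hypothesis test on OS, and no OS threshold drives a decision. With 20 events and a median of 6 months, an approximate 95% interval is 6 × exp(±1.96/√20), or 3.9 to 9.3 months, which is wider than the shift.

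All of this stands as a limit on size. It does not give a reason to make inclusion in a survival analysis depend on a later assessment, and it leaves the missing origin and the conflict between sections in place.

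**Conclusion.** The concern holds in a limited form. The mITT rule can remove early deaths from OS. Under the week-8 reading and exponential OS, the loss is up to about 19% of dosed participants at a median of 6 months and 7% at 17.5 months, with a median raised by up to about 1.8 months. These figures are towards the upper end, and the effect is near zero if any visit qualifies. The plan does not say which reading applies. The FAS result is not biased by early deaths; it lacks only a rule for undosed participants. The sections that require mITT OS and the subsection that names the FAS alone need to be reconciled. No error rate or sample size is affected, since OS is a descriptive secondary endpoint in cohorts of about 20.

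**What to change.** In Protocol 9.3.3 and in SAP 3.2, 6.2.4 and the Overall Survival subsection, state that Part 2 OS is reported on the Safety Analysis Set, counted from first dose. Delete the mITT OS analysis. List any participants enrolled but never dosed separately.

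Keeping the FAS and counting from the enrolment date would also resolve the origin mismatch, and is a reasonable alternative if the sponsor prefers an all-enrolled set. The mITT OS analysis should be dropped in either case.

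The cost is wording in two documents and one fewer analysis. OS may look slightly less favourable than it would on the mITT set.
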